---

### **Objective of the Study:**

Traffic-related air pollution (TRAP) is the predominant contributor to poor air quality in developed countries. The 4% of the US population-(Boehmer et al., 2013) who reside near busy roadways, as well as those who travel on them, are exposed to elevated concentrations of TRAP – a mixture of gases and particulate matter (PM) enriched in fuel combustion byproducts, as well as no tailpipe emissions. These exposures can be an order of magnitude higher than urban background exposure (Karner et al., 2010).

Both residential proximity to roadways and short-term exposures from time spent on roadways have been associated with adverse cardiovascular indicators and outcomes (Brook et al., 2010a). Peters et al (Peters et al., 2004) showed in a case-crossover study that exposure to TRAP was associated with myocardial infarction within 1 to 2 hours. Ghosh et al (Ghosh et al., 2016) reported that residential proximity to major roadways and traffic density were responsible for 2.4% and 6.8% of coronary heart disease and deaths, respectively, in Los Angeles and neighboring counties. Living near roadways has also been linked to increased prevalence of hypertension and increases in blood pressure (BP) (Brook et al., 2010b; Cai et al., 2016).

Controlled exposure to diesel particles and concentrated ambient fine PM (PM2.5;  
defined as particles with aerodynamic diameter <2.5  $\mu\text{m}$ ) from near-roadway locations has been shown to raise BP within 2 hours (Bellavia et al., 2013; Cosselman et al., 2012; Mills et al., 2011; Urch et al., 2005). There is also evidence that the particulate

component of TRAP is the causal agent. For example, Mills et al (Mills et al., 2011) reported that diesel exhaust exposure impaired vascular function but that filtered diesel exhaust (that retained its gaseous components) or pure carbon nano-PM did not. Similarly, Cosselman et al (Cosselman et al., 2012) reported a rapid increase in systolic BP (SBP; peaking 30–60 minutes from the start of exposure) but not diastolic BP (DBP) or heart rate (HR), upon exposure to diesel exhaust. In contrast, studies of the effects of short-term exposures to gaseous components of TRAP mixtures on cardiovascular function and BP are scarce. In the few studies we were able to find, the associations with adverse effects for O3 exposure are mixed (Li, 2018), while current evidence does not support an adverse acute effect of NO2 on vascular function (Langrish et al., 2010).

There have been over 90 studies assessing short-term effects of ambient ultrafine particles (UFPs; particles with aerodynamic diameter <100 nm and a component of TRAP) on cardiovascular indicators and outcomes (Ohlwein et al., 2019). There are also a growing number of long-term studies of UFP and health, with a particular focus on residential proximity to roadways, but these studies have reported mixed findings in terms of associations with cardiovascular health (Aguilera et al., 2016; Lane et al., 2016). Relatively few have studied short-term effects of TRAP, or its specific components such as soot (or black carbon [BC]) and UFP, on BP (Magalhaes et al., 2018).

It is difficult to draw causal relationships between TRAP and BP because of the observational nature of epidemiological studies, which include uncontrolled confounders, such as noise (Aguilera et al., 2016; Brauner et al., 2008; Brugge & Goble,

2002; Lane et al., 2016; Magalhaes et al., 2018; Morishita et al., 2018; Ohlwein et al., 2019) and exposures are often estimated based on central-site measurements, which introduces exposure error. Controlled exposure studies offer the potential to test associations under highly scripted and characterized conditions. However, studies with exposure concentrations that are realistically encountered proximate to highways are lacking. Furthermore, evaluation of the effectiveness of strategies to mitigate TRAP exposures, such as use of commercially available, stand-alone HEPA filtration, have, to date, shown limited benefits on BP and peripheral blood inflammation (Brauner et al., 2008; Brugge & Goble, 2002; Morishita et al., 2018). Morishita et al (Morishita et al., 2018) found reductions in SBP in older adults living in an urban area with 3-day use of HEPA filtration, which also reduced indoor PM2.5, but PM2.5 is not a marker of TRAP emissions. Therefore, the aim of our study was to assess whether reducing TRAP exposure by limiting indoor infiltration and deploying HEPA filtration for a short duration could have a beneficial effect on BP.

## **Methods:**

### **Study Design and Participants**

The study design was a 3-exposure, 3-period crossover trial in which participants attended three 2-hour-long exposure sessions (1 each for low, medium, and high exposure in random order), all on same day of the week, separated by 1-week washout periods. Twenty-four sessions of each type were held, and participants were assigned to the exposure sessions using a Latin square design. Two to 4 participants attended each exposure session.

The inclusion criteria were age of 40 to 75 years and speaking either English or Chinese. The exclusion criteria were self-reported history of a major cardiovascular outcome (including myocardial infarction, stroke, and angina), other serious health problems (chronic obstructive lung disease or current asthma), taking antihypertensive medications, smoking or living with a smoker, cognitive impairment, working at a job with high-combustion exposure (eg, taxi/truck driver and restaurant cook), and high-combustion exposure in the preceding 24 hours (such as driving on a highway). The Tufts University Social Sciences institutional review board approved the study protocol.

Participants were instructed to avoid caffeine, to not drive, and to avoid exposure to traffic other than what was necessary to get from their home to the study location on the morning of exposures. Participants were preferentially recruited from neighborhoods close to the study locations that have outdoor TRAP levels similar to the exposure session location. Most participants walked; however, a few were transported to short distances in gasoline-powered cars driven with the in-vehicle air recirculation fan turned on to limit exposure before arrival. Before the first exposure, participants were oriented to what to expect during the sessions to reduce stress reactions. Exposure session type was not disclosed to the participants.

Participants arrived 15 to 20 minutes before the start of each exposure session. Upon arrival, they completed a questionnaire that assessed exposures that could potentially affect their BP. Measures included the validated 16-item Perceived Stress Scale, self-reported taking of any medications (day and hour last taken), location and activity for each hour in the preceding 48 hours, consumption of caffeine or alcohol past midnight

the previous night, and vigorous physical activity in the last 24 hours by hour. If an exposure of concern was identified, which was rare, the participant was rescheduled.

## **Air Quality and Outcome Measures and Exposure Room Configuration**

### **Air Quality Measurements**

Particle number concentrations (PNC) and black carbon (BC) concentrations were monitored continuously. PNC was measured using a water-based condensation particle counter (TSI, Inc; model 3873;  $d_{50}=7$  nm) at 1-second resolution and BC concentration was measured with an aethalometer (Magee Scientific; model AE16) at 1-minute resolution. For the first half of the sessions, temperature was measured centrally in the room, and for the latter half of the sessions, temperature was measured directly adjacent to each study participant with a temperature logger (Onset Computer Corporation; model HOBO UX100-003).

### **Particle Size Distribution**

Particle size distributions in a subset of exposure sessions (subset session count: low, 8; medium, 9; and high, 7) were measured with a Scanning Electrical Mobility Spectrometer (Brechtel Manufacturing, Inc). The particle counter operated with butyl alcohol as the condensing fluid and to prevent detectable butyl alcohol scent, the particle counter was enclosed in an airtight box that was vented outdoors. The Scanning Electrical Mobility Spectrometer measured particles between 5 and 600 nm in 59 size

bins, executing a scan across the full-size range every 75 seconds. Average particle size distributions were generated for high-, medium-, and low-exposure sessions by averaging all scans over the 2-hour exposure session duration and then averaging the same exposure types.

### **BP and HR Measurement**

Participants were seated throughout the questionnaire (15 minutes) and exposure sessions (2 hours). During exposure, participants wore sound canceling headphones (Bose noise canceling wireless headphones), were instructed to refrain from doing anything, including reading or meditation, and asked not to fall asleep. If it appeared that a participant was falling asleep, which was rare (<5 instances), they were gently tapped and awakened. An ambulatory BP monitor (Suntech Oscar; Table S1) was placed on the dominant arm of participants and began recording at the start of each exposure session to record SBP, DBP, and HR every 10 minutes.

### **Exposure Room Configuration**

Exposure sessions were held at 2 near-highway locations (shown in Figure S1) where ambient air was enriched in TRAP. Most of the participants (n=63) attended exposure sessions in a ground-floor community room of a low-income housing development located near the intersection of I-90 and I-93 (average weekday daily traffic, 240 000 vehicles/day) in Chinatown, Boston. For the other 14 participants, sessions were conducted at another community room (on the ground floor in a multistory building) located in Somerville, MA, which was adjacent to I-93 and R38 (average weekday daily

traffic, 215 000 vehicles/day). Sessions were conducted in the morning (during 06:00–09:00 hours) to coincide with rush-hour traffic and lower atmospheric dispersion, that is, when TRAP concentrations were expected to be the highest (verified by diurnal trends measured at a vicinal near-highway regulatory monitoring site [ID: 25-025-0044]).

Three levels of exposure—low, medium, and high—were attained by varying the degree of ventilation (and thereby infiltration) and by increasing or decreasing the number or blower setting of HEPA filtration units. Two brands of HEPA air filters were used at both locations: IQ Air Health Pro (1 unit) and Austin Air Healthmate 400 (up to 7 units with 4-stage filter, which also contained granular activated carbon and zeolite).

Based on air quality measurements before the exposure sessions, we determined that a concentration of ≈20 000 to 30 000 particles/cm^3 could be expected during the high-exposure sessions and 10-fold lower concentrations could be attained in the low-exposure sessions. We targeted 33–50% lower than high-exposure concentrations, that is, 10 000 particles/cm^3, for the medium-exposure sessions.

During low exposure, infiltration of outdoor air into the room was minimized by closing doors and sealing the cracks underneath with duct tape. Neither exposure room had operable windows. Filtration of TRAP was maximized by continually running air filters (4 units at the Somerville location and 8 units at the larger Chinatown location).

During medium exposure, infiltration was restricted by closing doors, but cracks underneath were left unsealed. Filtration was optimized to maintain indoor PNC in the 8000- to 12 000-particles/cm^3 range by using 0 to 4 air filters.

During high exposure, infiltration was maximized by cross-ventilating the rooms by partially opening the doors that connected the room directly to outdoors and in the Somerville location, by adding a fan in addition to door opening (since cross-ventilation was not an option in that room). Air filters were not used during high exposures.

Both community rooms were located within a block of restaurants, which resulted in a noticeable odor during the last 30 to 45 minutes of some sessions when restaurants began cooking. Odor was only perceivable in some of the high-exposure sessions because this configuration allowed odors into the rooms.

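### Does the mismatch between a 33–50% reduction and 10 000 particles/cm³ for medium exposure call for a change to the plan?

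*Combined protocol and SAP*

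**What the plan says.** All of the target figures are in the Exposure Room Configuration section of the combined protocol and SAP.

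- **High exposure.** From air measurements made before the sessions, "we determined that a concentration of ≈20 000 to 30 000 particles/cm"³ "could be expected during the high-exposure sessions and 10-fold lower concentrations could be attained in the low-exposure sessions".
- **Medium exposure, as a reduction.** "We targeted 33–50% lower than high-exposure concentrations, that is".
- **Medium exposure, as a concentration.** The same sentence continues "that is, 10 000 particles/cm"³.
- **Medium exposure, as operated.** Two paragraphs later: "Filtration was optimized to maintain indoor PNC in the 8000- to 12 000-particles/cm"³ range, using between 0 and 4 air filters, with doors closed and the cracks beneath them left unsealed.

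The Statistical Analysis Plan section tests the dose-response effect of filtration with a linear contrast and gives no coefficients. Its model for blood pressure includes particle number and black carbon as time-varying covariates, and these two quantities are also analysed as outcomes in their own mixed model. The Air Quality Measurements section says both were monitored continuously.

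**The concern.** The sentence presents a percentage and a concentration as the same thing. Read literally they are not: a reduction of 33–50% from most of the expected high range ends well above 10 000 particles/cm³. The three exposure levels are the intervention, and this sentence is where the target for the middle one is given.

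Two consequences would matter if the percentage were in use. A team repeating the study from the percentage could run the middle level at up to twice 10 000. A reader judging whether low, medium and high are evenly spaced, which bears on how a linear dose-response contrast is read, would reach different answers from the two halves of the sentence.

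**Working it through.** **Inputs**, all from Exposure Room Configuration: high level H of about 20 000 to 30 000 (25 000 taken as the midpoint); low level H/10; medium target 33–50% lower; medium target 10 000; medium operating band 8000 to 12 000 (all particles/cm³).

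**Step 1. Try to reproduce 10 000 from the percentage.** A literal reduction gives H × (1 − 0.50) to H × (1 − 0.33). The reduction that 10 000 represents is 100 × (1 − 10 000/H).

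| H | 33–50% lower than H | Reduction at 10 000 | 10 000 as a share of H |
|---|---|---|---|
| 20 000 | 10 000–13 400 | 50.0% | 50.0% |
| 25 000 | 12 500–16 750 | 60.0% | 40.0% |
| 30 000 | 15 000–20 100 | 66.7% | 33.3% |

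The plan's 10 000 is reproduced only at 50% below 20 000. At H = 30 000 the literal target is 15 000/10 000 = 1.5 to 20 100/10 000 = 2.0 times the stated concentration.

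**Step 2. Look for a reading that fits.** The last column runs from 33.3% to 50.0%, which is the stated percentage range. The percentage fits as a share *of* the high level, and does not fit as a reduction *from* it.

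**Step 3. Compare with the operating band.** The midpoint is (8000 + 12 000)/2 = 10 000, the stated target. The band is 40–60% below 20 000 (1 − 12/20 and 1 − 8/20) and 60–73% below 30 000 (1 − 12/30 and 1 − 8/30). A literal 33–50% reduction falls partly inside the band only while 0.50 × H ≤ 12 000, that is, for H up to 24 000. Over the remaining (30 000 − 24 000)/(30 000 − 20 000) = 60% of the expected high range the two do not overlap.

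**Step 4. Trace where the percentage is used.**

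- *Running the sessions.* The medium level was held by adjusting filters to a band stated in absolute concentration. The percentage plays no part in that.
- *Linear contrast.* No coefficients are given and none are linked to target concentrations. If the usual equally spaced coefficients (−1, 0, 1) were used, which is an assumption, the medium level has weight zero and its target cannot enter the estimate.
- *Covariates and exposure analysis.* These use measured particle number and black carbon, not targets.

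**Step 5. Size the spacing argument.** Take H = 25 000 and low = 25 000/10 = 2500. The position of the medium level between low and high is (medium − 2500)/(25 000 − 2500).

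- At 10 000: 7500/22 500 = 33%.
- At 12 500: 10 000/22 500 = 44%.
- At 16 750: 14 250/22 500 = 63%.

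The two statements do describe differently spaced targets. An analyst who wanted spacing on the concentration scale would have the measured session concentrations for it and would not need the target.

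**The case for a change.** The strongest case for acting is that the error is certain, concerns the definition of an exposure level, and would take about one sentence to put right. The approximation sign on the high range cannot turn 50–67% into 33–50%. Over most of the expected high range the percentage and the operating band do not meet at all. In a study whose aim is to learn whether lowering exposure helps blood pressure, the sentence also understates the planned reduction.

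All of that arithmetic stands. The consequences do not follow from it. The factor of two needs a high level of 30 000 together with a 33% reduction; at 20 000 the ratio is 1.0 to 1.34. It also needs a replicator to use the percentage while passing over the concentration in the same sentence and the band two paragraphs later. The size of the reduction that the trial tested is known from continuous monitoring, so it need not be inferred from a stated target. The claim that the middle level fixes the spacing of the contrast has no support in the Statistical Analysis Plan, so there is nothing to carry over into the description of the contrast.

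**Conclusion.** The inconsistency is genuine and clerical. Against an expected high level of 20 000 to 30 000, 10 000 particles/cm³ is 50–67% lower, where the text says 33–50%. The percentage, the 10 000 target and the 8000 to 12 000 band should be reconciled, and which wording was intended is for the sponsor to say. Because the percentage feeds no operating rule, model term, contrast or threshold, rewording it would alter neither what was done in the rooms nor any result, and no change to the plan follows.

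This rests on two points: that the medium sessions were run to the band as described, and that the contrast coefficients were not derived from the stated percentage. The documents state the first. They give no sign that the second fails, although they do not list the coefficients.

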### **Statistical Analysis Plan:**

A linear mixed model was used to analyze the 3-exposure, 3-period crossover design. The primary outcome measure is the change in systolic blood pressure from the beginning of each exposure session. Before calculating change scores in each exposure session, each participant's systolic blood pressure measurements was smoothed using a 3-time-period, centered moving average. A random intercept was included in the linear mixed model to account for the interdependence of the observations that arise by each participant attending each exposure session. In addition, the model included baseline systolic blood pressure, mean room temperature for each session, and 2 time-varying covariates, particle number count and black carbon concentrations. A Toeplitz covariance structure was used to characterize the interdependence of the observations over time. Period and carryover effects was assessed in the linear mixed model. The mean dose-response effect of filtration was assessed for statistical significance using a linear contrast. An identical approach was

used to analyze diastolic blood pressure and heart rate. Particle number count and black carbon concentrations was also analyzed using a linear mixed model with average room temperature as a fixed covariate and a Toeplitz covariance structure.

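### Smoothing systolic blood pressure before forming change scores, with no rule for the first reading, can put readings taken under exposure into the reference of the primary outcome

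*Combined protocol and SAP*

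**What the plan says.** The section Statistical Analysis Plan defines the outcome as follows: "The primary outcome measure is the change in systolic blood pressure from the beginning of each exposure session". The next sentence fixes the order of operations. "Before calculating change scores in each exposure session", each participant's "systolic blood pressure measurements was smoothed using a 3-time-period, centered moving average".

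The section BP and HR Measurement says that the ambulatory monitor "began recording at the start of each exposure session to record SBP, DBP, and HR every 10 minutes". No reading before the session is described.

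On the model, the SAP says that "A random intercept was included in the linear mixed model" and that "the model included baseline systolic blood pressure, mean room temperature for each session, and 2 time-varying covariates, particle number count and black carbon concentrations". It does not say how the first or last reading is smoothed. It also does not say whether the reference for the change scores, or the baseline covariate, is raw or smoothed. The same approach is "used to analyze diastolic blood pressure and heart rate".

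**The concern.** A centred three-reading window needs one reading on each side. At time 0 there is nothing on the left, so the analyst must choose a rule, and the plan names none. Every usual rule that smooths the first value borrows at least the 10-minute reading, which is taken under the session's exposure. The reference is then no longer SBP at session start, and it can itself differ between the low, medium and high sessions.

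The reference is subtracted from every change score, so any exposure effect it contains is removed from the whole session. The stakes are an understated contrast for SBP, and for diastolic pressure and heart rate as well. A covariate labelled baseline may also be partly post-exposure. While the rule is unstated, a reader cannot tell which outcome was analysed.

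**Working it through.** The plan gives no figure on this point, so there is nothing to reproduce. The check derives the reference under each rule and asks how much of an effect it holds.

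**Inputs from the documents:** a three-reading centred window applied before change scores; first reading at session start; 10-minute spacing; 2-hour sessions.

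**Assumed:** readings at both ends, giving 13 readings at 0, 10, …, 120 minutes; and an exposure effect rising linearly from zero at time 0 to a plateau at T minutes, e(t) = min(t/T, 1). Values of T of 30 and 60 are used because the background section (Objective of the Study) cites a diesel-exhaust study with an SBP peak at 30 to 60 minutes. That section gives neither an onset time nor a duration.

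**Step 1. Share of the plateau effect in the reference** = w0·e(0) + w10·e(10) + w20·e(20).

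For T = 30: e(0) = 0, e(10) = 1/3, e(20) = 2/3. For T = 60: 0, 1/6, 1/3.

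| Rule for the first value | Weights on 0, 10, 20 min | Share, T = 30 | Share, T = 60 |
|---|---|---|---|
| Full windows only | 1/3, 1/3, 1/3 | (1/3 + 2/3)/3 = 33% | (1/6 + 1/3)/3 = 17% |
| Shortened window | 1/2, 1/2, 0 | 1/6 = 17% | 1/12 = 8% |
| Padded (first value repeated) | 2/3, 1/3, 0 | 1/9 = 11% | 1/18 = 6% |
| Raw first reading | 1, 0, 0 | 0% | 0% |

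A reflected window (1/3, 2/3, 0) would give 2/9 = 22% and 1/9 = 11%.

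**Step 2. Effect on the change scores.** Without baseline adjustment, the change at plateau is 1 minus the share. For T = 30 that is 67%, 83%, 89% and 100% in the table's order; for T = 60 it is 83%, 92%, 94% and 100%. With full windows the first available change score, at 20 minutes, is (10 + 20 + 30)/3 − (0 + 10 + 20)/3, where each number stands for the reading at that minute. It reduces to one third of the 30-minute minus the 0-minute reading.

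**Step 3. When nothing is lost.** If the effect starts after 20 minutes, e(10) = e(20) = 0 and the share is zero under every rule. With no effect, e(t) = 0 throughout and there is no bias.

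**Step 4. Baseline adjustment.** Let β be the slope of change on the baseline covariate.
- If the covariate is the same smoothed reference, the adjusted contrast subtracts (1 + β) × share. For full windows and T = 30, the plateau contrast retained is 67% at β = 0, 1 − 0.5 × 1/3 = 83% at β = −0.5, and 100% at β = −1. These slopes are illustrative.
- If the covariate is the raw time-0 reading while the reference is smoothed, the covariate has no expected difference between exposures in this setup. The adjustment then restores nothing in expectation.

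So the size of the attenuation also depends on the baseline definition, which the SAP leaves open.

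**The case against.** The strongest reply is that the harm is doubly conditional: an averaged rule must have been used, and the effect must begin within 20 minutes. The first reading may well have been left raw, in which case the reference is unaffected. The cited peak at 30 to 60 minutes concerns diesel exhaust and does not establish an early onset in this setting. Any bias of this kind is toward zero, and baseline adjustment can shrink it. All of this stands. It limits the size of the point but does not supply the missing rule.

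A second reply is that the shares describe the change scores, not the planned model. That model also adjusts for particle number, black carbon and room temperature. If the exposure acts through the pollutants, the adjusted exposure contrast is a different quantity and the percentages do not carry over to it. This also stands, so no model-based recovery or power figure is offered here.

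A third reply is that smoothing is the authors' choice, and that stating the end-point rule would be enough. Stating it would remove the ambiguity. It would not make an averaged reference agree with an outcome defined from session start.

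A reader might infer that the trial's SBP contrast was in fact attenuated. The documents do not support that, because they do not show which rule was applied. Nor do they support a claim that a raw reference is more precise.

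**Conclusion.** The point holds in a conditional form. Taken literally, the stated order of operations puts the 10-minute reading, and with full windows the 20-minute reading, into the reference of an outcome defined from session start. Only a raw first reading avoids this, and the SAP does not say that one was used.

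If the effect begins within 20 minutes, 6% to 33% of a plateau effect reached at 30 to 60 minutes sits in the reference under the full, shortened or padded rule, before baseline adjustment. This rests on the assumed 13-reading grid and the assumed linear rise. The gap in the plan is certain; its effect on the result is not known. Severity is minor to moderate.

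**What to change.** State in the SAP that change is measured from the unsmoothed time-0 reading of the same session, and that this reading is also the baseline covariate. Smooth only the later readings, with windows that exclude time 0 or with a stated end-point rule, and state the rule for the last reading too. Apply this to SBP, diastolic pressure and heart rate. Report the averaged-reference version, with its rule, as a sensitivity analysis. The SAP is written largely in the past tense; if the analysis has been run, disclose the rule that was used.

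Also state whether the room was already at its session condition, with participants present, in the 15 to 20 minutes between arrival and session start. If it was, the time-0 reading is not free of exposure either.

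The cost is wording and a re-run, with no new data. A single-reading reference is usually somewhat noisier. In simulations over 24 assumed variance settings, fitted by likelihood without the pollutant and temperature covariates, the standard error with the raw reference was about 6% to 9% higher at the median, depending on the averaged rule compared. The ratio ranged from 0.59 to 1.59, so precision can move either way. The settings cross autocorrelations of 0, 0.3 and 0.6 with participant/session/reading SDs in mmHg of 12/6/6, 12/4/8, 12/8/5, 12/2/8, 12/1/8, 12/3/6, 8/4/6 and 16/6/8; none of these is in the documents. The case for the change is agreement with the stated outcome, not gain in precision.

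### Two to four people share each exposure session, but the model names no session term, so the standard error of the exposure contrast may be too small

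*Combined protocol and SAP*

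**What the plan says.** Under Exposure Room Configuration, the three levels are created for the room as a whole with doors, sealing, a fan and HEPA units. For the low level, for example, "infiltration of outdoor air into the room was minimized by closing doors and sealing the cracks underneath with duct tape". Everyone present receives the same condition.

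Under Study Design and Participants: "Twenty-four sessions of each type were held, and participants were assigned to the exposure sessions using a Latin square design". The next sentence reads: "Two to 4 participants attended each exposure session".

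The Statistical Analysis Plan section describes these parts of the blood-pressure model:

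- a random intercept "to account for the interdependence of the observations that arise by each participant attending each exposure session";
- baseline systolic pressure, "mean room temperature for each session, and 2 time-varying covariates, particle number count and black carbon concentrations";
- a within-person time structure: "A Toeplitz covariance structure was used to characterize the interdependence of the observations over time";
- an assessment of period and carryover effects, and a linear contrast across exposure levels as the test.

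The same approach is "used to analyze diastolic blood pressure and heart rate". For none of the three outcomes does the section name a session, date or group effect, or a cluster-robust variance.

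**The concern.** When a condition is applied to a room, anything else particular to that room on that morning is also shared by the people in it. The random intercept and the Toeplitz structure both describe how one person's readings relate to each other. Even if the intercept is read as one per person per session, two people in the same session are independent given the covariates.

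The crossover does not remove the problem. A group effect that is constant over the three weeks cancels in the within-person comparison. A session-specific effect does not cancel, whether groups stayed together or were reshuffled between weeks.

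The change score and the covariates take out part of what co-attendees share, but not necessarily all of it. The protocol names one shared factor that is not a model term: "Odor was only perceivable in some of the high-exposure sessions because this configuration allowed odors into the rooms".

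At stake are the standard error, confidence interval and p-value of the exposure contrast for systolic pressure, diastolic pressure and heart rate. The point estimate is not called into question here.

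**Working it through.** The documents state no sample-size calculation, significance level or ICC, so there is no figure of the plan's to reproduce. The check is how far the standard error would be off over a range of assumed ICCs.

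**Inputs from the documents**

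- Participants: 63 + 14 = 77 (Exposure Room Configuration).
- Sessions: 24 per level, 24 × 3 = 72 in all, with 2 to 4 people in each (Study Design and Participants).
- Mean attendance: 77 × 3 / 72 = 3.21 per session, inside the stated 2 to 4.

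**Assumptions**

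- Two-sided 5% test; all 77 people attend all three sessions.
- ICC means the share of the non-participant variance of a person's session-mean blood-pressure change that is common to the session, after the covariates. It is not the ICC of single 10-minute readings.

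**Effective cluster size.** The relevant size is m = Σn² / Σn, where n is the number of people in a session. For 24 sessions of 2 to 4 people totalling 77:

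- most even (19 of 3, 5 of 4): (171 + 80) / 77 = 251 / 77 = 3.26;
- most uneven (9 of 2, 1 of 3, 14 of 4): (36 + 9 + 224) / 77 = 269 / 77 = 3.49.

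**Formulas**

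- Design effect: DEFF = 1 + (m − 1) × ICC
- True SE / model SE = √DEFF
- Actual type I error = 2 × [1 − Φ(1.96 / √DEFF)]
- Effective participants per level = 77 / DEFF

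For example, with ICC 0.10 and m = 3.26: DEFF = 1 + 2.26 × 0.10 = 1.226; √1.226 = 1.107; 1.96 / 1.107 = 1.77; type I error = 7.7%.

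| Assumed ICC | DEFF | True SE / model SE | Type I error | Effective participants |
|---|---|---|---|---|
| 0.01 | 1.023–1.025 | 1.011–1.012 | 5.3% | 75.1–75.3 |
| 0.05 | 1.113–1.125 | 1.055–1.061 | 6.3–6.5% | 68.5–69.2 |
| 0.10 | 1.226–1.249 | 1.107–1.118 | 7.7–8.0% | 61.6–62.8 |
| 0.20 | 1.452–1.499 | 1.205–1.224 | 10.4–10.9% | 51.4–53.0 |

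Using the plain mean of 3.21 instead of 3.26 moves only the lower ends, to 7.6% at ICC 0.10 and 10.3% at ICC 0.20. At ICC 0.20 the model SE is 1 − 1/1.205 = 17% to 1 − 1/1.224 = 18% too small.

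**Simulation.** Person-session means were simulated for 77 people and 24 sessions per level, with groups kept together or reshuffled between weeks (4,000 trials per setting, Monte Carlo error about 0.3–0.5 points). With a participant intercept only, type I error was:

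- 4.8–5.2% at ICC 0;
- 5.1–5.6% at 0.01;
- 5.6–6.8% at 0.05;
- 7.0–8.8% at 0.10;
- 9.9–10.6% at 0.20.

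With a session random intercept and Satterthwaite degrees of freedom, it was 3.9–5.6% in all 20 settings (five ICCs, two size layouts, two grouping arrangements). The simulation contains no repeated readings, Toeplitz structure or covariates. It checks the clustering arithmetic, not the full planned model.

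**The case against.** The best reply is that nothing in the documents shows a material residual correlation, and every figure above rests on an assumed ICC. At 0.05 or below, the standard error is at most about 6% too small relative to the truth and type I error at most 6.5% by the formula. No basis is given for a value as high as 0.20.

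The design also limits what co-attendees can share. They sat throughout with noise-canceling headphones and without reading or meditating. Sessions fell on the same weekday and between 06:00 and 09:00. Participants were oriented beforehand, and were rescheduled if a prior exposure of concern came up. Odor is a weak example: it arose in the last 30 to 45 minutes of some sessions and was noticed only at the high level, so it is partly a question of bias. A constant session intercept may also fit poorly if a shared influence builds up during the session. Finally, a one-paragraph summary may not be the full specification.

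Much of this stands as a limit on size. The ICC is unknown, 0.20 is an illustrative upper case, and the design features make large values less likely. They do not make the ICC zero, and a model without a session term assumes zero and cannot test it. No other section supplies the missing term. The contrast concerns the mean response, so the session-average component is what chiefly drives its standard error, and a session intercept captures that component.

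**Conclusion.** The concern holds, in its conditional form. Exposure is assigned to sessions of two to four people, and the model as described treats those people as independent given their own intercept and the covariates. To the extent that their adjusted blood-pressure changes are positively correlated, the interval for the linear contrast is too narrow and the test rejects too often.

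The effect is negligible at an ICC near zero, minor up to about 0.05 and material from about 0.10. This rests on the assumed ICC range, a two-sided 5% test and complete attendance by all 77. The documents do not allow a choice within the range, and that is itself a reason to estimate the session variance. The same conclusion applies to diastolic pressure and heart rate.

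**What to change.** - Add a random intercept for session (72 sessions) alongside the participant intercept in the models for systolic pressure, diastolic pressure and heart rate.
- State whether the same people attended together in all three weeks. If groups were reshuffled, session is crossed with participant. If groups stayed together, add a group effect too. A stable group effect cancels in the contrast, but modelling it keeps stable group differences out of the session variance.
- Use Kenward-Roger or Satterthwaite degrees of freedom for the linear contrast.
- Report the estimated session variance for each outcome. If it is near zero, the conclusions stand and the reader can see why.

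**Cost.** The SAP wording changes. Because the section is written in the past tense, three models probably have to be re-run with an extra variance component. Session attendance must have been recorded. Intervals widen by about 1% at ICC 0.01 and by 20–22% at ICC 0.20. With an ICC of 0 to 0.01 the test becomes slightly conservative (simulated type I error 3.9–4.6%).

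This does not deal with odor as a possible confounder of the high level, which is a separate question.
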